### 3.5.3.6. Alcohol Intake

For the entire study population, alcohol intake will be assessed 1 of 3 ways; with only 2 of these being databased and reported –

1. %CDT – reported using descriptive summary statistics over time
2. Total score on interview-based AUDIT questionnaire – reported using description summary statistics over time
3. Participants' self-reported intake of alcohol-containing drinks *[not databased]*

## 4. ANALYSIS SETS (POPULATIONS FOR ANALYSIS)

Data for all participants will be assessed to determine if participants meet the criteria for inclusion in each analysis population prior to unblinding and releasing the database and classifications will be documented per standard operating procedures.

All analyses will be performed on an “as-treated” basis and will not include data from participants who are randomized but not treated.

If a participant takes a treatment that is not consistent with the treatment they are randomized to, for example, error in dispensation of blister cards relative to assigned made by IRT, then they will be reported under the treatment that they actually receive (so called actual treatment) for all safety, PK and PD analyses, where applicable.

A full list of protocol deviations will be compiled and reviewed to identify major deviations, which may potentially impact inclusion in the applicable estimand, prior to database lock and release.

*For purposes of analysis, the following analysis sets are defined:*

Participants Analysis Set	Description
Enrolled	All participants who sign the preQ ICD.
Randomly assigned to investigational product	All participants randomly assigned to IP, on Day 1/Visit 4, regardless of whether or not study intervention was administered.
Evaluable	All participants randomly assigned to IP and who take at least 1 dose of IP. Participants will be analyzed according to the randomized intervention.
Safety	All participants randomly assigned to IP and who take at least 1 dose of IP. Participants will be analyzed according to the treatment arm they actually received.
Defined Population for Analysis	Description
PK Concentration Set	All participants randomly assigned to study intervention and who take at least 1 dose of DGAT2i + ACCi and in whom at least 1 concentration value is reported.

Note: Analysis set for Part 2 is envisioned to be identical to Part 1.

## 5. GENERAL METHODOLOGY AND CONVENTIONS

Data from Parts 1 and 2 will be pooled for purposes of summarizing/analyzing end-of-study results and will be reported from placebo followed by ascending order of the DGAT2i to ACCi total daily dose (TDD) ratio (mg:mg).

In case the same co-administration ratio for BID and QD dosing regimen is evaluated, data will be reported 1st for BID and then QD while still in the ascending order for DGAT2i to ACCi TDD ratio (mg:mg).

### 5.1. Hypotheses and Decision Rules

Not applicable

### 5.2. General Methods

#### 5.2.1. Analyses for Binary Endpoints

Not applicable

#### 5.2.2. Analyses for Continuous Endpoints

Continuous endpoints and relevant safety endpoints will be presented using summary statistics: number of randomized participants, number of participants contributing to summary, arithmetic mean, standard deviation, median, minimum and maximum values.

### **5.2.3. Analyses for Categorical Endpoints**

Categorical endpoints and relevant safety endpoints will be presented using summary statistics: number of randomized participants, number of observations, counts and percentages.

### **5.2.4. Analysis of Covariance (ANCOVA)**

The effect of DGAT2i + ACCi on primary, secondary, and tertiary endpoints at Week 6 will be analyzed using ANCOVA approach.

#### **Analysis of change from baseline:**

The ANCOVA model will include the change from baseline of the relevant endpoint as specified in [Section 6](#) as the dependent variable and will include treatment as a fixed effect and baseline as a covariate.

Missing values will not be imputed.

The Least Squares Means (LSMeans) together with 80% confidence intervals and standard errors will be obtained for each treatment. Differences in LSMeans between each treatment and placebo, together with 80% confidence intervals and standard errors, will also be obtained.

Standard SAS output will be provided to support the main statistical summary table for the models.

Example SAS code is provided in Appendix 3.

#### **Analysis of percent change from baseline:**

The ANCOVA model will include the natural logarithmic transformed of relative change from baseline of the relevant endpoint as specified in [Section 6](#) as the dependent variable and will include treatment as a fixed effect and baseline as a covariate.

Missing values will not be imputed.

The adjusted geometric Least Squares Means (LSMeans) together with 80% confidence intervals and standard errors will be obtained for each treatment. Differences in adjusted geometric LSMeans between each treatment and placebo, together with 80% confidence intervals and standard errors, will also be obtained. All LSMeans and LSMeans differences (including CI's) will be back transformed to provide adjusted geometric LSMeans and ratios of adjusted geometric LSMeans. Then, percent change from baseline will be calculated as follows:

$$\text{Percent change} = 100 * (\text{RCBL} - 1)$$

where RCBL is either the adjusted geometric LSMeans estimate or the ratio of adjusted geometric means coming from the statistical model. The corresponding 80% CIs will be calculated as well.

Standard SAS output will be provided to support the main statistical summary table for the models.

Example SAS code is provided in Appendix 3.

### 5.2.5. Longitudinal Analysis

The effect *over time* of DGAT2i + ACCi on secondary, and tertiary endpoints (see list in [Section 3](#)) will be analyzed using a Mixed-Model Repeated Measures (MMRM) approach with treatment, week and treatment by-week interaction as fixed effects, participant as random effect. An unstructured covariance matrix will be used to estimate the variances and covariance within participants across time points. If convergence is not obtained or model fit is not adequate, other covariance structures will be investigated as necessary. The Kenward-Roger approximation will be used for estimating degrees of freedom for the model parameters. Missing values will not be imputed as part of the MMRM model assumptions.

Baseline (in raw scale or log scale depending on the endpoint) will be included as covariate in the model.

#### **Analysis to report percent change from baseline:**

MMRM models will include the natural log transformed of relative change from baseline (RCBL) of the relevant endpoints as specified in [Section 6](#).

The adjusted geometric Least Squares Means (LSMeans) together with 80% confidence intervals and standard errors will be obtained for each treatment and week. Differences (and corresponding confidence intervals) between LSMeans estimates will be obtained comparing treatments for each week. All LSMeans and LSMeans differences (including CI's) will be back transformed to provide adjusted geometric LSMeans and ratios of adjusted geometric LSMeans. Then, percent change from baseline will be calculated as follows:

$$\text{Percent change} = 100 * (\text{RCBL} - 1)$$

where RCBL is either the adjusted geometric LSMeans estimate or the ratio of adjusted geometric means coming from the statistical model. The corresponding 80% CIs will be calculated as well.

Standard SAS output will be provided to support the main statistical summary table for the models.

Example SAS code is provided in Appendix 3.

#### **Analysis of change from baseline:**

MMRM models will include change from baseline (CFB) of the relevant endpoints as specified in [Section 6](#).

The Least Squares Means (LSMeans) together with 80% confidence intervals and standard errors will be obtained for each treatment and week. Differences (and corresponding

confidence intervals) between LSMeans estimates will be obtained comparing treatments for each week.

Standard SAS output will be provided to support the main statistical summary table for the models.

Example SAS code is provided in Appendix 3.

### **5.3. Methods to Manage Missing Data**

**For the analysis of safety endpoints**, the sponsor data standard rules for imputation will be applied.

#### **5.3.1. Deviations, Missing Concentrations and Anomalous Values**

In summary tables and plots of median profiles, statistics will be calculated having set concentrations to missing if 1 of the following cases is true:

1. A concentration has been collected as ND (ie, not done) or NS (ie, no sample),
2. A deviation in sampling time is of sufficient concern or a concentration has been flagged anomalous by the pharmacokineticist.

Note that summary statistics will not be presented at a particular time point if more than 50% of the data are missing.

#### **5.3.2. Pharmacokinetic Parameters**

- Missing pharmacokinetic data will be treated as such and no imputed values will be derived when presenting descriptive statistics at scheduled assessments.
- In all data presentations (except listings), concentrations below the limit of quantification (BLQ) will be set to zero. In listings BLQ values will be reported as “<LLQ”, where LLQ will be replaced with the value for the lower limit of quantification.

#### **5.3.3. Pharmacodynamic Parameters**

- Missing data for ***all*** the pharmacodynamic parameters will be treated as such and no imputed values will be derived when presenting descriptive statistics at scheduled assessments.
- Concentrations below Lower Limit of Quantification (LLQ) will be set to half-LLQ (ie LLQ/2) for summary outputs; in listings BLQ values will be reported as “<LLQ”.
- Derived data by calculation (eg indirect bilirubin) will not follow the rule described above and will be reported as <LLQ (in listings) with a derived value of (<negative value> minus 0.0001 = positive value) when generating summary statistics, as required.
- Any values above the Upper Limit of Quantification (ULQ) will be assigned to the ULQ for display purposes in Figures and for computation of summary statistics; in listings ULQ values will be reported as “>ULQ”.
- Observed cases will be used when analyzing continuous variables using Mixed-Model Repeated Measures (MMRM), analysis of covariance (ANCOVA) and nonlinear models.

## 6. ANALYSES AND SUMMARIES

### 6.1. Primary Endpoint

#### 6.1.1. Liver Fat Content Assessed Using MRI-PDFF at Week 6

- Estimand strategy: Estimand 1

Raw data, changes from baseline, and percent changes from baseline will be summarized by treatment, and week as described in [Section 5.2.2](#).

- Figures for summary Outputs:
  - ✓ Box and whisker plots for individual percent change from baseline at Week 6 versus treatment will be presented and overlaid with arithmetic means. Only box, whiskers, median, arithmetic mean, and outliers should be reported in this graphic.

The statistical analysis will be performed using the natural-logarithmic transformation of relative change from baseline as described in [Section 5.2.4](#).

- Statistical outputs:
  - ✓ Adjusted geometric LSMeans estimates with 80% confidence interval for each treatment along with the translation in percent change (with their associated confidence interval),
  - ✓ Ratio of adjusted geometric LSMeans estimates for each active treatment against placebo and the corresponding 80% confidence interval along with the translation in percent difference (with their associated confidence interval). P-values for the ratio of adjusted geometric LSMeans estimates for each active treatment against placebo will be reported as well,
  - ✓ Summary tables reporting MMRM outputs will include the number of participants included in the analysis.
- Figures from statistical outputs
  - ✓ Plot of percent change from baseline after back transformation of adjusted geometric LSMeans with 80% confidence interval over time,
  - ✓ Plot of percent change from baseline placebo-adjusted after back transformation of adjusted geometric LSMeans ratios with 80% confidence interval over time.

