## 2.1. Study Rationale

The current study is an extension of a recently concluded study (C3711001) assessing placebo, DGAT2i alone (300 mg BID), ACCi alone (15 mg BID), and coadministration of DGAT2i + ACCi for a treatment duration of up to 6 weeks in participants with NAFLD. In Study C3711001, a placebo-adjusted LS mean reduction in liver fat of  $\geq 35\%$  was observed in all active groups. In addition, on average, the increases in fasting serum triglyceride levels observed with ACCi alone were mitigated by coadministration with DGAT2i. It is anticipated that via coadministration of DGAT2i + ACCi, hepatic lipid metabolism will be modulated in distinct and complementary ways, potentially resulting in greater efficacy than DGAT2i administered alone. However, whether the effect on primary pharmacology can be maintained along with mitigation of ACCi-induced elevation in fasting serum triglycerides via lower doses of DGAT2i as well as QD administration of both agents remains to be tested and forms the purpose of the current study. While Study C3711001 population included participants with NAFLD, population in the current study is proposed as *presumed NASH*, as defined by the Sponsor as participants meeting all of following via *double-confirmation* between the PreQ and SCR visits:

- Liver fat as assessed via quantitative ultrasound parameter CAPTM of  $\geq 280$  dB/m, assessed using FibroScan®;
- Liver stiffness as assessed via quantitative ultrasound parameter VCTETM of  $\geq 7$  kPa, assessed using FibroScan®;
- Presence of *at least 2* of the 5 concomitant medical conditions which are associated with NAFLD – refer to criterion # 3 in [Section 5](#); and
- ALT  $>$  ULN (and  $\leq 5 \times$  ULN).

In the current study, a 2-part design with sequential conduct of Part 1 and Part 2 with each part conducted in distinct/separate cohorts of participants is proposed. While the overall study design, objectives/endpoints, eligibility criteria for both parts are envisioned to remain identical, data from Part 1 will be used to determine whether to conduct Part 2. Observed data from Part 1 will guide the selection of doses and dosing regimens (ie, QD vs BID) of DGAT2i + ACCi coadministration evaluated in Part 2.

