#### 4.2. Scientific Rationale for Study Design

Reduction in hepatic steatosis with DGAT2i alone, ACCi alone, and DGAT2i + ACCi have been shown in participants with NAFLD with dosing of the intervention for as little as 2 weeks (DGAT2i alone), 6 weeks (DGAT2i alone plus DGAT2i + ACCi), and up to 16 weeks (with ACCi alone). The current study is an extension of a recently concluded study (C3711001) assessing placebo, DGAT2i alone (300 mg BID), ACCi alone (15 mg BID), and coadministration of DGAT2i + ACCi, for a treatment duration of 6 weeks in participants with NAFLD. The current study is designed to find the lowest dose of DGAT2i which will mitigate ACCi-induced elevations in fasting serum triglyceride, while maintaining effectiveness (as assessed via reduction in hepatic steatosis). Data from Part 1 will dictate conduct of, the doses, and the dosing regimens (ie, QD vs BID) of DGAT2i + ACCi, potentially evaluated in Part 2.

In this study, 2 separate informed consents will be obtained: the first consent is limited to PreQ visit activities only; and the second consent is for the main study only (from Screening through participant completion/Early Termination) in those deemed to meet eligibility criteria based on non-invasive procedures completed at PreQ. Between the PreQ and SCR visits, many of the non-invasive procedures and clinical laboratory tests assessed are identical. This is motivated by the intent to confirm that the population progressed to Run-In/Visit 2 is consistently characterized as Sponsor-defined presumed NASH. As a measure of additional diligence and as an attempt to remove variability due to laboratory-to-laboratory differences, the clinical laboratory tests assessed at PreQ and SCR are proposed to be analyzed by the Sponsor-identified central laboratory. The assessments to narrow the population ultimately progressed to Run-In/Visit 2 consist of ***double-confirmation*** between assessment at PreQ and SCR of: (a) blood-based markers of liver function (ie, ALT, AST, alkaline phosphatase, total bilirubin) and ensuring participants have stable results (defined by  $\leq 50\%$  variability in ALT/AST/alkaline phosphatase plus total bilirubin  $\leq$  ULN, unless Gilbert's syndrome); ***and*** (b) a constellation of clinical and liver imaging characteristics which are highly suggestive of a NASH diagnosis (in the absence of a liver biopsy) referred to as Sponsor-defined presumed NASH.

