ACCi alone is not planned for evaluation in this study given the previously described undesirable changes in fasting serum triglycerides encountered with liver-targeted ACC inhibitors and their potential implications for long term cardiometabolic health.

In this study, based on a combination of thorough medical history (including assessment of ethanol intake and administration of the *interview-version* of the AUDIT-10 -item questionnaire), and clinical laboratory tests (ie, %CDT), medically qualified site-staff will be required to rule out alcohol based as well as and/or other causes of hepatic steatosis/inflammation/fibrosis, and ensure that the population enrolled is confirmed, as best as possible, to have Sponsor-defined presumed NASH. These assessments (AUDIT and %CDT) will be re-assessed prior to randomization and at end of dosing to confirm that while in the study alcohol intake remained in moderation. Participants with previously confirmed genetic polymorphisms, for example, PNPLA3 carriers, are eligible given that these polymorphisms are known to modify/increase risk for steatohepatitis but do not by themselves cause steatohepatitis.

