### 4.3. Justification for Dose

#### 4.3.1. Part 1

In Part 1, a range of doses of DGAT2i will be coadministered with fixed dose of ACCi (20 mg/day). Doses selected (refer to [Table 3](#)) were based on the observed effect on liver fat following 2 weeks of dosing with DGAT2i in Study C2541005, 6 weeks of dosing of DGAT2i alone, ACCi alone, and coadministration in Study C3711001, as well as 16 weeks of dosing with ACCi alone in Study C1171002.

In Study C3711001, administration of DGAT2i 300 mg BID and ACCi 15 mg BID alone and when coadministered over 6 weeks in participants with NAFLD, a placebo-adjusted LS mean reduction in liver fat of  $\geq 35\%$  was observed in all groups. In addition, on average, fasting serum triglyceride increases observed with ACCi alone were mitigated by coadministration with DGAT2i. In the current study, coadministration of DGAT2i + ACCi (at a ratio of 20:1) was selected as the highest dose; it contains the same DGAT2i dose assessed in Study C3711001 (DGAT2i 300 mg BID + ACCi 15 mg BID; at a ratio of 30:1) though a slightly lower ACCi dose (10 mg BID) is proposed in the current study acknowledging that while mitigation of ACCi-induced effect on fasting serum triglycerides with coadministration of DGAT2i was seen, this response had an upper 90% CI of an increase of 28% in placebo-adjusted change from baseline for DGAT2i + ACCi, in Study C3711001.

The lower doses of 50 mg/day and 200 mg/day of DGAT2i, administered BID (ie, 25 mg BID and 100 mg BID), in this study are proposed in order to assess the dose-response for mitigation of ACCi-induced elevations in fasting serum triglycerides, as well as to assess the effect of these coadministered doses on liver steatosis. Given that DGAT2i decreases PCSK9 with an ED50 of 7 mg BID and that PCSK9 is a marker of SREBP activity (mechanism postulated to be responsible for the DGAT2i-mediated mitigation of ACCi-induced elevations in fasting serum triglycerides), it is possible that doses significantly lower than 300 mg BID may mitigate ACCi-mediated lipid changes. Spacing of the DGAT2i doses by 3-4 fold allow for covering a 12-fold range of DGAT2i doses (ie, 50 to 600, mg/day).

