### **9.2. Sample Size Determination**

#### **9.2.1. Part 1**

The proposed sample size for this study is approximately 90 participants randomized (18 participants per group) to ensure at least 75 participants (15 participants per group) offer evaluable data. With a sample size of 15 completers per group and with natural log-transformed SD of 0.221 for liver fat (assessed via MRI-PDFF), a 25% placebo-adjusted liver fat decrease can be detected at a significance level of 5% 1-sided with a power >90%.

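### The aim concerns DGAT2i dose, but the listed liver-fat and triglyceride results compare each arm only with a placebo that carries no ACCi; list the B/E and C/E ratios as well

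*SAP*

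**What the plan says.** Protocol 4.2 describes the study as "designed to find the lowest dose of DGAT2i which will mitigate ACCi-induced elevations in fasting serum triglyceride, while maintaining effectiveness". Protocol 4.3.1 adds that the lower DGAT2i doses were chosen to assess dose-response for that mitigation. Both statements compare DGAT2i doses with one another.

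Protocol Table 3 gives the Part 1 arms. A is placebo for both agents. B, C and E combine DGAT2i 25, 100 and 300 mg BID with ACCi 10 mg BID. D is DGAT2i 300 mg QD with ACCi 20 mg QD. Each active arm therefore receives ACCi 20 mg/day. Protocol 4.2 states that "ACCi alone is not planned for evaluation in this study" and gives a reason.

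The analysis text runs against placebo:

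- SAP 5.2.4 (ANCOVA) provides "Differences in adjusted geometric LSMeans between each treatment and placebo".
- SAP 6.1.1 lists, for liver fat, "Ratio of adjusted geometric LSMeans estimates for each active treatment against placebo and the corresponding 80% confidence interval", with p-values.
- SAP 6.2.1 lists the same ratios and p-values for triglycerides at each time point.
- The objectives and both main estimands (Protocol 3 and 9.1.1; SAP 2.1) are also worded relative to placebo.

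No formal hypothesis test is planned (Protocol 9.1.2), and SAP 5.1 marks decision rules as not applicable. The listed outputs contain no active-versus-active ratio, dose trend or lowest-dose criterion.

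**The concern.** A contrast of DGAT2i + ACCi with placebo measures the combination as a whole. It cannot say how much of a liver-fat effect comes from DGAT2i, or whether a lower DGAT2i dose keeps what the highest dose achieves. This matters because ACCi alone is active on liver fat: Protocol 2.1 says of the preceding study, which included ACCi 15 mg BID alone, that a placebo-adjusted reduction of at least 35% "was observed in all active groups".

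Arms B, C and E hold ACCi dose and frequency fixed and differ only in DGAT2i dose. The comparison that isolates DGAT2i dose is therefore already in the design. What is missing is a listed ratio with its interval. Without one, the study report could show every arm beating placebo on liver fat and still leave the dose question to informal reading across rows.

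**Working it through.** **Inputs.** From Protocol 9.2.1: "natural log-transformed SD of 0.221 for liver fat", 15 completers per group, a 25% placebo-adjusted decrease, 5% one-sided, power above 90%. The SD is taken as the residual SD of the ANCOVA. Residual df = 75 − 5 arms − 1 covariate = 69.

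**The plan's own figure.** SE of a two-arm difference = 0.221 × √(2/15) = 0.0807. Effect = −ln 0.75 = 0.2877. Power = Φ(0.2877/0.0807 − 1.645) = 97.3% (97.0% with a noncentral t on 69 df). This agrees with the stated >90%.

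**Separation from placebo if DGAT2i adds nothing.** If ACCi alone gives 35%, the effect is −ln 0.65 = 0.431, and 0.431/0.0807 = 5.3 SE. The 35% was seen at 30 mg/day in NAFLD, so for 20 mg/day in presumed NASH a range is needed. The joint probabilities come from 400,000 simulated trials with four active arms sharing one placebo arm and a pooled SD on 69 df.

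| Assumed reduction from ACCi 20 mg/day alone | One arm separates (5% one-sided) | All four separate (5% one-sided) | All four 80% intervals exclude no effect |
|---|---|---|---|
| 35% | 99.99% | 99.9% | >99.9% |
| 30% | 99.7% | 99% | 99.7% |
| 25% | 97.3% | 91% | 96% |
| 20% | 86.9% | 67% | 81% |
| 15% | 64.4% | 34% | 50% |

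**What B/E or C/E would deliver for liver fat.**

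- Interval: t(0.90, 69 df) × 0.0807 = 0.104 on the log scale, so the 80% interval is the ratio ×/÷ exp(0.104) = 1.11.
- Separating two doses: suppose B gives a 35% reduction and E gives 40%, 45% or 50% (assumed). Power = Φ(ln[0.65/(1 − e)]/0.0807 − 1.645), where e is the reduction in E. This gives 26%, 66% or 95%.
- Showing that the lower dose retains the effect: with a true ratio of 1 and margin m (assumed), power = Φ(ln m/0.0807 − 1.645). For m = 1.15, Φ(0.1398/0.0807 − 1.645) = 53%. For m = 1.20, Φ(0.1823/0.0807 − 1.645) = 73%.
- A linear log-dose trend across B, C and E has almost the same power as B versus E in the separation scenarios: 26%, 67% and 95%.

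The documents give no SD for triglycerides, so the matching size cannot be computed for that endpoint.

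**The case against.** Much of the opposing case stands.

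- A reader might infer that the plan contains no comparison except against placebo. That is exact for the liver-fat ANCOVA text and outputs only. SAP 5.2.5 provides MMRM differences between treatments at each week without restricting them to placebo, and the example code in Appendix 3 requests all pairwise differences. Neither is carried into a listed result.
- A reader might infer that the reported analysis cannot inform dose choice. That goes too far. LS means with standard errors are produced for every arm, so B/E as a point ratio, and roughly its interval, can be worked out by hand. Protocol 4.1.2 has the interim review consider mitigation across the dose ratios. Protocol 9.5.1 and SAP 7.2 feed PK/PD output into the Part 2 decision. Protocol 9.5 also leaves decision criteria to an interim or final SAP; SAP 7.2 states none, and an interim SAP may exist that is not public. Population PK/PD work, if conducted, is reported outside the main study report (Protocol 9.4.4).
- A reader might infer that mitigation should be judged against arm E instead of placebo. The documents do not support that. Protocol 4.3.1 itself judges the earlier result by placebo-adjusted change, with an upper 90% limit of a 28% increase. Placebo is the right reference for whether triglycerides remain raised, and E may itself leave them raised.
- The objectives and estimands are worded against placebo, so the SAP is consistent with them. The aim as phrased in the synopsis could also be met if ACCi drives most of the fat reduction and a low DGAT2i dose controls triglycerides. The mismatch is with the maintained-effect wording of Protocol 4.2 and the dose-response purpose in 4.3.1.

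**Conclusion.** The point holds as a gap in the listed results: the contrast that isolates DGAT2i dose at a fixed ACCi dose and frequency has no listed ratio or interval for either liver fat or triglycerides.

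The size depends on what ACCi 20 mg/day does alone in this population, which the documents do not report. If it gives 25% or more, all four arms separate from placebo on liver fat with probability 91% or higher even when DGAT2i adds nothing. At 15% this falls to 34%, so near-certain separation in every arm is an assumption and not a finding. Separation here means a one-sided 5% comparison; the plan defines no pass rule.

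It is also tempting to expect the B/E interval to settle whether a lower dose keeps the effect. At 15 per arm it will not do so reliably: ×/÷1.11 is informative, but power is 53% or 73% at assumed margins of 1.15 or 1.20. The added contrasts are estimates to be read beside the placebo contrasts. This is a cheap improvement that brings the reported results closer to the stated aim; it does not invalidate the design.

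**What to change.** In SAP 5.2.4, 6.1.1 and 6.2.1:

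1. List B/E and C/E with 80% intervals from the models already fitted, for MRI-PDFF at Week 6 and for triglycerides at each week.
2. Add a DGAT2i dose trend across B, C and E as supportive only. A straight line in log dose may fit poorly if the response plateaus, which is possible given the low PCSK9 ED50 (7 mg BID) cited in Protocol 4.3.1.
3. Report D/E separately, labelled as a comparison of regimen as well as dose, because D differs from E in the dosing frequency of both agents.
4. State the roles. The placebo contrasts show the effect of the combination and whether it leaves triglycerides raised. The B, C, E contrasts describe what DGAT2i dose contributes. All are estimates without multiplicity adjustment.

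No ACCi-alone arm, new data or extra participants are needed. The example code already requests pairwise differences, but its alpha = 0.1 gives 90% intervals, so the level must be set to match the 80% text. The cost is SAP wording and a modest number of unadjusted intervals: with triglycerides at Weeks 2, 4, 6 and Follow-up (Protocol 9.4.2), 3 ratios × (1 + 4) = 15, plus the trend.
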